This human laboratory study will systematically determine the independent and interactive effects of expectancy and nicotine dose on reinforcing (behavioral economic demand), subjective, and topography outcomes. Participants (N=20) will complete 4 experimental sessions in which expectancy (labeling of “average” nicotine versus “very low” nicotine) and nicotine dose (15.8 mg/g versus 0.4 mg/g) are manipulated as within-subject variables. Participants will sample a study cigarette of these combinations at the start of each session and complete craving, mood, withdrawal, and subjective drug effect measures before and after smoking. Smoking topography will also be collected during cigarette administration to determine if expectancy and dose impact how one smokes – one way that cognitive or pharmacological effects can impact smoking behavior. Demand will be evaluated with an incentivized demand task using experienced outcomes to improve experimental rigor. Behavioral economic demand analyses will differentiate between effects attributable to consumption of a good at no or little cost (“demand intensity”) and consumption following increases in cost (“demand elasticity”).

4. Study Procedures

a. Study design, including the sequence and timing of study procedures (distinguish research procedures from those that are part of routine care).

General Overview

Participants reporting current tobacco cigarette use will complete this double-blind, within-subject laboratory study. Participation will require in-person screening and 5 laboratory sessions that will take over approximately 2 weeks. We plan to recruit up to 25 participants to fully complete the study and will enroll up to 32 participants to account for possible attrition. Potential volunteers will participate in a brief telephone screening after responding to posted advertisements (e.g., community postings, radio). Those meeting initial inclusion/exclusion criteria in telephone

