Participants will complete demand procedures following the standardized cigarette administration (see details below).. A three hour smoking period will follow demand task completion in which cigarette units purchased at a randomly selected price from the demand task are available to smoke. Topography will be collected during this time, but will not be directly compared across sessions due to differences in the number of cigarette units obtained across participants and sessions depending on demand task selections. Sessions will conclude after the 3-hour period. Following completion of all experimental sessions (or earlier if participation is discontinued), participants will be debriefed about the study and experimental manipulations. Prior to debriefing, the validity of the expectancy blind and delivery will be assessed by asking participants what they believed the study purpose was. Participants will also be asked about the estimated nicotine content of cigarettes at the end of each session to evaluate validity of the manipulation.

Description of Behavioral Economic Demand

An ***incentivized purchase task*** will be used to evaluate demand involving within-session incentivized consequences. The purchase task procedure is a well-validated experimental procedure with meta-analyses supporting concurrent validity (González-Roz et al., 2019) and sensitivity to experimental manipulations (Acuff et al., 2020). The current study will use a procedure with experienced consequences to improve rigor. Participants will receive a study income (\$50 of the \$100 session payment) to allocate for purchasing. Instructions will stipulate that one price will be randomly selected to be *real*—meaning that the cigarette units purchased at the selected price will be available to consume during a 3-hour period and money deducted from the total session payment. Instructions will stipulate that these will be the only cigarettes available during that time and that cigarettes cannot be stockpiled (i.e., will only be available for consumption in the laboratory).

Study Cigarettes

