- Positive urine screening for illicit drugs other than cannabis or current substance use disorder (other than nicotine). Non-daily cannabis use will be allowed given increasing prevalence of cannabis use in the U.S. (Hasin, 2018). Exclusion of any cannabis use by

participants is considered a threat to external validity and inclusion of persons who use cannabis non-daily should not alter the risk profile of the study.

- Women who are pregnant, plan to become pregnant, or are breast-feeding.
- Medical contraindications to receiving tobacco products (e.g., cardiovascular disease) as assessed through a physical and self-report history.

5. Drugs/ Substances/ Devices

a. The rationale for choosing the drug and dose or for choosing the device to be used.

The Family Smoking Prevention and Tobacco Control Act 2009 gave FDA authority to limit cigarette nicotine levels to reduce levels of nicotine dependence and therefore increase smoking cessation rates and decrease the overwhelming morbidity and mortality associated with smoking (Benowitz and Henningfield, 1994). Studies have suggested reduced nicotine cigarettes result in decreased nicotine intake (Benowitz et al. 2007; Donny et al., 2015) and decreased nicotine dependence (Donny et al., 2015). Doses were selected to approximate market nicotine levels (15.8 mg/g) and reduced-nicotine cigarettes recently authorized by the FDA for commercial sale (0.4 mg/g; Moonlight brand at 0.2-0.7 mg/g). Menthol or non-menthol cigarettes will be used based on participant typical brand.

b. Justification and safety information if FDA approved drugs will be administered for non-FDA approved indications or if doses or routes of administration or participant populations are changed.

N/A

c. Justification and safety information if non-FDA approved drugs without an IND will be administered.

N/A

6. Study Statistics

a. Primary outcome variable.

Behavioral economic demand curve metrics during each experimental session

- a. Q0 (demand intensity)
- b. α (demand elasticity)

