Demand tasks will be analyzed for derived and curve-observed measures. Derived measures include demand intensity (Q0; consumption at unconstrained price) and demand elasticity (a measure of sensitivity of consumption to changes in price) and will be computed using the exponential demand equation $\text{LogQ} = \text{Log Q0} + k(e^{-\alpha Q0C}) - 1$ (Hersh & Silberberg, 2008). The independent variable C is cost (price/cigarette), the dependent variable Q is consumption (cigarettes purchased at a particular price), the scaling parameter k indicates the range of LogQ in the observed data. Free parameters are Q0 (demand intensity) and α (demand elasticity). Should zero-dense data be observed, a modified exponentiated form of the demand equation will be considered (Koffarnus et al., 2015; Strickland et al., 2016). Observed measures include Pmax (price at maximum consumption), Omax (maximum consumption), and breakpoint (Breakpoint-1; the price of last non-zero demand).

b. Secondary outcome variables. Descriptions of Outcome Measures

Subjective Effect Measures

Subjective effect measures will include a measure of nicotine withdrawal (MNWS), smoking craving (QSU), mood (PANAS), and cigarette subjective experience (Drug Effect Questionnaire). These measures will be collected upon arrival to the laboratory (i.e., immediately prior to cigarette administration) and following the 10-minute standardized smoking period. All measures will be scored using standard procedures.

Smoking Topography

Six measures of smoking topography will be collected including: total puff volume, mean puff volume, mean puff duration, mean inter-puff interval, mean maximum flow rate, and number of puffs (Higgins et al., 2018). These measures will be collected during the 10-minute standardized cigarette smoking period using a custom smoking topography system currently in use in our laboratory.

c. Statistical plan including sample size justification and interim data analysis.

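### Section 6a: Omax and Pmax as worded do not measure peak spending, and the printed demand equation contradicts the plan's own definition of Q0 unless k = 1

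*Combined protocol and SAP*

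**What the plan says.** Section 6a (Primary outcome variable) gives the primary outcome as "Behavioral economic demand curve metrics during each experimental session" and lists two: Q0 and alpha. It then sets out the following.

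- **Consumption:** "the dependent variable Q is consumption (cigarettes purchased at a particular price". This is a quantity, not money.
- **Intensity:** "demand intensity (Q0; consumption at unconstrained price". The Background (section 3) agrees, tying intensity to "effects attributable to consumption of a good at no or little cost".
- **Equation, as printed:** log Q = log Q0 + k(e^(−alpha·Q0·C)) − 1, where C is price per cigarette. Q0 and alpha are the free parameters.
- **Scaling constant:** "the scaling parameter k indicates the range of LogQ in the observed data". No value is given, and the text does not say whether one k serves all curves.
- **Additional measures:** "Observed measures include Pmax (price at maximum consumption), Omax (maximum consumption), and breakpoint", with breakpoint glossed as "the price of last non-zero demand".

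No other section defines Omax or Pmax, fixes k, or prints the equation a second time.

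**The concern.** There are two separate points in the same paragraph.

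**Omax and Pmax.** Because consumption is a count of cigarettes, its maximum on a demand schedule normally sits at the lowest price. Omax then restates what was bought there, and Pmax says little or nothing about how purchasing responds to price. A report that follows these definitions would carry one redundant measure and one that could rank conditions misleadingly.

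**The equation.** With the −1 outside the bracket, the parameter called Q0 is no longer consumption at zero price unless k happens to equal 1. Q0 and alpha are the two primary outcomes, and section 6c presents the study as a pilot whose results will inform later projects. Mis-scaled values could therefore be carried forward.

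**Working it through.** The documents give no price list or purchase data, so the schedules below are assumed. Logs are taken to base 10.

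**1. Omax and Pmax.** Assumed prices: 0, 0.25, 0.5, 1, 2, 3, 4, 5, 7.5, 10.

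- Schedule C buys 6, 5, 5, 5, 5, 5, 4, 4, 3, 3. Spending (price × number) is 0, 1.25, 2.50, 5, 10, 15, 16, 20, 22.50, 30.
- Schedule D buys 6, 6, 6, 6, 4, 3, 2, 1, 0, 0. Spending is 0, 1.50, 3, 6, 8, 9, 8, 5, 0, 0.

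| Measure | C | D |
|---|---|---|
| Omax as worded | 6 | 6 |
| Pmax as worded, lowest price | 0 | 0 |
| Pmax as worded, highest tied price | 0.00 | 1.00 |
| Maximum spending | 30.00 at price 10 | 9.00 at price 3 |
| Breakpoint | 10 | 5 |
| alpha (bracketed form, zeros excluded, shared k = log10 6 = 0.778) | 0.0081 | 0.0408 |

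Spending, breakpoint and alpha all show C as the less price-sensitive. Omax as worded cannot separate the two. Pmax as worded either ties or, on the highest-tied-price reading, puts them in the opposite order. Spending of 30.00 is within the $50 study income in section 4a, so schedule C is feasible.

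**2. The equation at zero price.** Put C = 0 in the printed form: log Q = log Q0 + k − 1, so Q(0) = Q0 × 10^(k−1). The ratio Q(0)/Q0 is 0.32 at k = 0.5, 1 at k = 1, 3.16 at k = 1.5, 10 at k = 2 and 100 at k = 3. With the −1 inside the bracket, Q(0) = Q0 for every k, as the definition requires.

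**3. What the printed form does to the estimates.** The two forms describe the same curve when

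- log Q0(printed) − 1 = log Q0 − k, so Q0(printed) = Q0 × 10^(1−k); and
- alpha(printed) × Q0(printed) = alpha × Q0, so alpha(printed) = alpha × 10^(k−1).

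If k is the log range of purchases and the smallest non-zero purchase is 1, then k = log10(largest purchase). The factors become 10/largest for Q0 and largest/10 for alpha:

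| Largest purchase | Q0 factor | alpha factor |
|---|---|---|
| 6 | 1.67 | 0.6 |
| 10 | 1 | 1 |
| 20 | 0.5 | 2 |
| 30 | 0.33 | 3 |

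Curves generated from the bracketed form with Q0 = 6, 10, 20 and 30, alpha = 0.02 and k = log10 Q0, then refitted with the printed form, all return Q0 = 10. Their alphas are 0.012, 0.020, 0.040 and 0.060, as the table predicts.

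**4. Effect on the tests.** With shared k = 0.778, fitting C and D both ways gives identical residual cost (0.00463 and 0.05097). Q0 moves from 5.55 to 9.25 for C and from 6.97 to 11.61 for D, a factor of 1.667 each; alpha is multiplied by 0.6 in both. A common factor cancels from the F ratios on the raw scale, and after a log transform it only adds a constant. The 2×2 ANOVA results do not change. Equally, goodness of fit would not reveal the problem.

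**5. Why a shared k should be stated.** Take purchases of 6, 6, 6, 5, 5, 4, 4, 3, 3, 2 against 6, 6, 6, 5, 4, 4, 3, 2, 1, 0 at the same prices.

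- Bracketed form, shared k: Q0 is 6.20 versus 6.59, and alpha 0.0139 versus 0.0297.
- Bracketed form, k set per curve (0.477 and 0.778): alpha is 0.0285 versus 0.0297, so the difference nearly vanishes.
- Printed form, k set per curve: Q0 is 20.74 versus 10.98, which reverses the order.

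**The case against.** A fair defence runs as follows.

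- **The bracket may not be the authors' error.** It could come from typing or from conversion of the PDF, and the intended form can be recovered from the definition of Q0. This stands, and it is why the source file should be checked first. It does not touch Omax and Pmax, which are defined in plain words.
- **The planned tests are unaffected.** This stands if one k is shared, which is the more natural reading of the text. Only the reported values are then wrong, and they can be corrected once k is known.
- **Omax as worded is not numerically the same as fitted Q0.** This is true: it is 6 for both schedules, while fitted Q0 is 5.55 and 6.97. The redundancy is with observed purchasing at the lowest price, and it requires that purchases never rise with price.
- **The plan never says these measures should reflect spending.** This also stands. The spending definition is a proposed repair, not something the documents state. Even so, the measures as worded add almost nothing about response to price.
- **The reversal in Pmax depends on chosen schedules and a tie rule.** Agreed. On the lowest-price reading there is no reversal, only an uninformative tie. Spending in schedule C also peaks at the highest assumed price, so its true peak may lie beyond the list.
- **No hypothesis rests on Omax or Pmax.** Correct: the primary outcomes are Q0 and alpha, and alpha and breakpoint still cover price sensitivity.

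**Conclusion.** The concern holds, and it is minor. For any schedule in which purchases do not rise with price, Omax as worded is lowest-price purchasing and Pmax carries little or no price information. That follows from the text alone; the schedules only illustrate its size.

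The printed equation is incompatible with the stated meaning of Q0 unless k = 1. Under the assumption of a smallest non-zero purchase of 1, reported Q0 would be off by a factor between 1.67 and 0.33 for largest purchases of 6 to 30 cigarettes, and alpha by the reciprocal. There is no error at 10. With a shared k, inference on the primary outcomes is unaffected. If the bracket proves to be a conversion fault, the Omax and Pmax point remains on its own.

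**What to change.** In section 6a:

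1. Define Omax as maximum expenditure (price × cigarettes purchased) and Pmax as the price at which expenditure is greatest. The purchase task in section 4a already yields what is needed: numbers bought at each price, with "money deducted from the total session payment" for the price drawn.
2. Check the equation against the source file. If the bracket is as printed, change it to log Q = log Q0 + k(e^(−alpha·Q0·C) − 1).
3. As a clarification, state that a single k is used for all participants and sessions.

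These are wording edits to one section. They need no new data and leave the ANOVA and the sample size as they are.

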screening will be scheduled for in-person screening at our research unit. Laboratory screening will include health history, drug history, and physical examination. Those passing full screening will participate in 1 practice session with procedures identical to experimental sessions but using the participant's own-brand cigarette. This practice session will serve to acclimate the participant to the study procedures, account for practice effects, and provide data for exploratory comparisons with own-brand cigarette data. Following practice sessions, each participant will complete 4 experimental sessions in which nicotine content (15.8 mg/g versus 0.4 mg/g) and expectancy (participant instructed "average" versus "very low" nicotine; see details below) are manipulated as within-subject variables. The full combination of sessions will be 15.8 told average; 15.8 told low; 0.4 told average; 0.4 told low completed in a randomized order.

Practice and Experimental Session Timeline

Participants will complete 4 experimental sessions lasting about 4 hours. Upon arrival to the laboratory, carbon monoxide will be collected to verify 8-hour abstinence as indicated by a CO <50% of the value obtained a screening (e.g., Mercincavage et al., 2016). A battery of subjective effect measures will be collected prior to cigarette administration including the Minnesota Nicotine Withdrawal Scale (MNWS; Toll et al., 2007), the Questionnaire on Smoking Urges (QSU; Cox et al., 2001), and the Positive and Negative Affect Scale (PANAS; Watson et al., 1988) measuring nicotine withdrawal, cigarette craving, and mood, respectively.

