Participants will then smoke one of that session's cigarette (15.8 mg/g or 0.4 mg/g). Participants will be instructed that this cigarette is either "the same level of nicotine as your usual brand" or "a very low level of nicotine compared to your usual brand" to harmonize with prior work on expectancy (Mercincavage et al., 2016). This manipulation will be necessary for the expectancy variable and success of the study protocol. A thorough debriefing about the study will occur at study completion or if a participant discontinues participation early. Dose will be double-blind such that neither research staff nor participants know the dose. Expectancy will be single-blind such that research staff who collect outcome assessments will not know the exposure participants receive (i.e., a separate member of research staff will deliver the manipulation). Participants will have 10 minutes to smoke the whole experimental cigarette. Topography will be collected including measures of total puff volume, mean puff volume, mean puff duration, mean inter-puff interval, mean maximum flow rate, and number of puffs using existing topography equipment. Subjective effect measures (MNWS, QSU, and PANAS) will be collected again following the 10-minute smoking period. Subjective effect measures about the experimental cigarettes will also be collected (i.e., 100-point visual analog scale drug effect measures such as "Strength" and "Satisfaction"). Physiological measures (e.g., CO) will be collected prior to and following cigarette administration.

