Primary Analysis: Low nicotine expectancy and low nicotine dose will result in lower demand with lowest demand in combination: Demand variables will be computed and transformed if non-normal (e.g., log-transform). Analyses will use a 2x2 repeated measures ANOVA with the within-subject factors of expectancy (“average” and “very low”) and dose (15.8 mg/g and 0.4 mg/g). Hypothesis 1 will be supported by significant main effects indicating significantly lower demand under “very low” expectancy and 0.4 mg/g conditions. A significant interaction would also indicate different-than-additive effects of expectancy and dose. Such an interaction is plotted in Figure 3 with hypothetical data of a greater reduction in demand intensity by nicotine content under the “very low” expectancy condition.

Secondary Analysis: Low nicotine expectancy and low nicotine dose will result in lower positive subjective effects (H2) and lower puff volume (H3) with lowest values in combination. A 2x2 ANOVA will also be used for puff topography and subjective effect measures with similar predictions as Hypothesis 1. Measures with pre- and post-cigarette administration measures will use a 2x2x2 ANOVA including a within-subject factor of time. We expect less reduction in withdrawal and craving with low nicotine expectancy and low nicotine dose indicated by significant interactions with time.

Sample Size Justification: With respect to power, simulation of a 2x2 repeated measure ANOVA based on estimates from preliminary demand data (e.g., nicotine dose effect, SD) identified 82% power to detect a main effect under additive effects. More generally, the sample provides 80% power to detect a medium-large bivariate within-subject effects ($d_z = 0.66$). This project is considered a pilot project and therefore we have focused on a feasible sample size to generate signals of the behavioral relevance for expectancy in reduced-nicotine policy to inform scientific rationale for future projects. These findings will also provide evidence for the feasibility of within-session procedures with incentivized consequences for rapidly evaluating demand of experimental commodities, thereby serving as preliminary “proof-of-concept” data for a variety of proposals evaluating the reinforcing effects of novel experimental commodities. We will enroll up to 25 participants that complete the study to ensure that at least 20 provide fully systematic data on primary demand outcomes.

d. Early stopping rules.

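### The primary analysis of Q0 and alpha leaves out the craving score taken before the cigarette in every session; this costs some precision but causes no bias

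*Combined protocol and SAP*

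**What the plan says.** Section 6.a defines the primary outcome as "Behavioral economic demand curve metrics during each experimental session", namely Q0 (intensity) and alpha (elasticity). Section 6.c, Primary Analysis, then states: "Analyses will use a 2x2 repeated measures ANOVA with the within-subject factors of expectancy (“average” and “very low”) and dose". Expectancy, dose and their interaction are the only terms.

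The session timeline in section 4.a describes the arrival procedures: "A battery of subjective effect measures will be collected prior to cigarette administration including the Minnesota Nicotine Withdrawal Scale". The same battery includes the QSU for craving and the PANAS for mood. Section 6.b confirms the timing: "These measures will be collected upon arrival to the laboratory (i.e., immediately prior to cigarette administration". Abstinence is checked by a single upper limit: "carbon monoxide will be collected to verify 8-hour abstinence as indicated by a CO <50% of the value obtained a screening". The label is described next, together with the cigarette ("Participants will be instructed that this cigarette is either" one of two nicotine levels), and the demand task follows the cigarette. The order of the four conditions is randomised.

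The only planned use of the pre-cigarette scores is the secondary 2x2x2 ANOVA, where time is a third factor.

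**The concern.** The within-subject design removes stable differences between smokers. It does not remove differences between one smoker's own sessions. Two arrivals can both pass the CO check with quite different craving, and if craving on the day influences purchasing, that variation inflates the error against which dose, expectancy and their interaction are tested. The classical repeated measures ANOVA has no place for a covariate that changes from session to session, so a measurement the trial already holds goes unused for the primary outcome.

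What is at stake is power in a small trial. Section 6.c plans for at least 20 participants with systematic demand data and claims 80% power only for a medium-large effect. Its separate 82% figure covers a main effect, whereas the primary objective in section 2 is the interaction.

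**Working it through.** **Inputs.** From section 6.c: n = 20, d_z = 0.66, power 80%. Alpha and sidedness are not stated; two-sided 0.05 is assumed. The within-person correlation r between pre-cigarette QSU and the demand metric is not in the documents, so a range is shown.

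**1. The plan's own figure.** Each effect in a 2x2 within-subject design is a one-degree-of-freedom paired contrast. Power comes from the noncentral t with n − 1 = 19 df and noncentrality d_z·√n = 0.66 × √20 = 2.95. This gives 79.95%, so the stated 80% reproduces. (One-sided testing would give 88.5%, which supports the two-sided reading.) The 82% figure cannot be rebuilt, because its effect and SD are not given.

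**2. After adjustment, equal contrast variances.** The covariate removes a fraction r² of the within-person variance, so d_z becomes 0.66/√(1 − r²). One further df is taken off (18) as a cautious allowance for the slope. The equivalent unadjusted n is 20/(1 − r²).

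| r | variance removed | adjusted d_z | power | equivalent n |
|---|---|---|---|---|
| 0 | 0% | 0.660 | 79.7% | 20.0 |
| 0.2 | 4% | 0.674 | 81.3% | 20.8 |
| 0.3 | 9% | 0.692 | 83.3% | 22.0 |
| 0.4 | 16% | 0.720 | 86.1% | 23.8 |
| 0.5 | 25% | 0.762 | 89.6% | 26.7 |

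Simulation of the recommended model (one common QSU slope, each effect tested against its own participant-by-effect error) agrees to within a point: about 79%, 81%, 83%, 86% and 89%, with type I error near 5%.

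**3. If participants differ in their response to dose.** Let the dose contrast have λ times the variance of the other contrasts, the excess being unrelated to craving. QSU then removes only r²/λ of the dose-contrast variance. With λ = 2 and r = 0.4 that is 0.16/2 = 8% instead of 16%. The adjusted d_z is 0.66/√0.92 = 0.688, so power is just under the 83.3% shown for 0.692, not 86.1%.

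**4. Why the error term matters.** Pooling the three contrast errors gives an expected variance of (λ + 2)/3, where the dose test needs λ. The standard error is then too small by a factor √[(λ + 2)/(3λ)]: 0.88, 0.82 and 0.75 for λ = 1.5, 2 and 3. With a critical value of about 2.00 (56 df), the effective cut-offs are 1.77, 1.64 and 1.49. By the normal approximation the two-sided type I error is about 7.7%, 10.2% and 13.5%. Simulation at n = 20, which does not treat the error variance as known, gives about 8–9%, 11–12% and 15%. The planned ANOVA stays at 5% throughout.

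**The case against.** The strongest case against acting is that nothing in the plan is wrong. The ANOVA is valid, its power statement matches it, and section 6.c describes a pilot of feasible size; with 25 completers the power at d_z = 0.66 would already be 88.6%. The correlation is entirely assumed. A whole cigarette, smoked over up to 10 minutes, comes between arrival craving and the demand task, and every session requires CO-verified abstinence. Both could keep r low, and at r = 0.2 the gain is about one point. All of this stands, and it limits how much can be promised. It does not remove the case for prespecifying a covariate that is already collected.

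A reader might infer more than the documents support, in three ways.

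- **That the primary result is biased or its type I error inflated.** It is not: the order of conditions is randomised, and the planned ANOVA tests each effect against its own error.
- **That any mixed model with a participant effect would be a safe improvement.** It would not be. A participant intercept with about 56 pooled residual df holds 5% only if all contrasts have equal variance. Nothing in the documents establishes that, and smokers may well differ in their response to nicotine dose.
- **That the pre-cigarette QSU is certainly unaffected by that session's condition.** Collection before the cigarette is explicit. Collection before the label is only implied by the order of the session narrative. If the label came first, QSU could itself be changed by expectancy.

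**Conclusion.** The point holds as a modest loss of efficiency. For r between 0.3 and 0.5 the gain is about 3 to 9 points of power at d_z = 0.66, equivalent to roughly 2 to 7 extra participants. At r = 0.2 it is about one point, and at r = 0 there is a loss of less than one point. These figures assume n = 20, two-sided 0.05, equal contrast variances and an r for which the documents give no value. The gain on the dose effect is smaller if participants differ in their response to dose.

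The adjustment is sound only if the QSU precedes the label. Centring on the person's mean also uses QSU from all four sessions, so it assumes that earlier conditions do not carry over into later arrival craving. Pilot status does not argue against the change: when n is fixed by feasibility, the analysis is the cheapest place to recover precision.

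**What to change.** In section 6.c, Primary Analysis:

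- Analyse transformed Q0 and alpha with expectancy, dose, their interaction and that session's pre-cigarette QSU total. Centre QSU within person, fit one common slope, and name it as the only covariate. Naming it in advance also prevents a later choice among QSU, MNWS, PANAS and CO.
- Keep participant-specific dose and expectancy effects in the model, so that each one-df effect is tested against its own participant-by-effect error (about 19 df at n = 20). Rule out a participant-intercept-only model with pooled error.
- Report the unadjusted 2x2 ANOVA alongside.

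In section 4.a, state that the label is given only after the pre-cigarette battery is complete, and in section 6.c that a QSU score taken after the label is not used as a covariate. The same statement protects the pre-cigarette score in the secondary 2x2x2 analysis.

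The cost is SAP wording, a slightly more complex model, and under one point of power if craving proves unrelated to demand. No new data, visits or participants are needed.
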